5.3 DRUG CONCENTRATION MEASUREMENTS AND PHARMACOKINETICS

Not applicable

5.4 ASSESSMENT OF BIOMARKER(S)

This section refers to exploratory biomarkers. Established biomarkers of efficacy and safety are described and discussed in sections [5.1](#) and [5.2](#).

Exploratory biomarkers will be analysed to provide clinical evidence of the biological mode of action of the combination of BI 765063 and ezabenlimab or BI 765063 and Pembrolizumab (i.e., pharmacodynamic biomarkers), to molecularly characterize an individual patient's cancer in neoadjuvant setting. Biomarker maybe useful to retrospectively correlate patient subgroups with differential responses to treatment and/or to prognosis. These analyses are hypothesis generating and will be used to expand the current understanding of the trial drugs and the disease. Participation in the biomarker testing is mandatory and is a prerequisite for participating in the study.

Should other tissues or blood-based biomarkers beyond those exploratory biomarkers in the [Flowchart](#) become relevant, these may also be explored. The list of biomarkers planned to be studied during the trial may change based on new information in the scientific literature or early trial analysis.

Any remaining samples or derived material from pre-specified analyses (RNA, DNA) will be destroyed no later than 5 years after the final trial report is archived.

The following biomarkers are planned to be examined in this trial (for detailed sampling times, refer to the [Flowchart](#)).

5.4.1 Biomarkers planned to be assessed in this trial

- Assessment of biomarkers of potential predictive value
 - SIRP α genotype (V1/V1, V1/V2, V2/V2), through WES/PCR
 - Baseline SIRP α and CD47 expression in tumor, through bulk RNAseq and scRNAseq
 - Baseline MMR/MSI status, TMB status, PD-L1 expression, T cell and macrophage infiltration in tumor through WES, bulk RNAseq, and MICSSS
- Pharmacological modulations of key MoA biomarkers upon Ezabenlimab/BI 765063 combination

Proprietary confidential information © 2022 Boehringer Ingelheim International GmbH or one or more of its affiliated companies

- Macrophage reprogramming in tumor (changes in macrophage phenotype from baseline) through bulk RNAseq and scRNAseq
- CD8 T cell infiltration in tumor, through MICSSS, bulk RNAseq and scRNAseq
- Changes of lymphoid/myeloid populations in tumor and in blood through CyTOF
- TCR clonality for clonal expansion/enrichment analysis in tumor and in blood through TCR sequencing on tissue and blood
- Longitudinal mutation analysis, baseline TMB from ctDNA analysis in blood
- MoA-related cytokine modulation
- Changes of microbiome in stool through 16s sequencing

5.4.2 Methods of Sample Collection, Handling of Samples and Biomarker Results

Detailed instructions for handling, storage, and shipment of the biomarker samples will be provided in the laboratory manual. All tumor and blood samples will be obtained at time points as defined in the [Flow Chart](#). Biomarker data performed by the laboratory could be reported to investigators upon request.

5.5 BIOBANKING

5.5.1 Methods and timing of sample collection

Detailed instructions on sampling, preparation, processing, shipment and storage are provided in the laboratory manual. For sampling time points see [Flow Chart](#).

The following biomarker samples specified in section [5.4](#), Assessment of Biomarkers, will be banked: pre-treatment and surgery tumor tissue, fixed in formalin and embedded in paraffin.

5.6 OTHER ASSESSMENTS

Not applicable

5.7 APPROPRIATENESS OF MEASUREMENTS

All measurements performed during this trial are standard measurements and will be performed in order to monitor patients' safety and to determine biological activity and efficacy in an appropriate way. The scheduled measurements will allow monitoring of changes in vital signs, standard laboratory values, and ECG parameters that might occur as a result of administration of trial medication. The safety assessments are standard, are accepted for evaluation of safety and tolerability of an intravenously administered drug, and are widely used in clinical trials.

6. INVESTIGATIONAL PLAN

6.1 VISIT SCHEDULE

Patients meeting the inclusion and exclusion criteria who have signed a written ICF are eligible for participation in the trial. Patients will visit the clinical site at the time points specified in the Flowchart. All patients should adhere to the visit schedule as specified in the Flowchart. The allowed windows for each visit and assessment are specified in the Flowcharts. Additional flexibility (e.g. to allow for public holidays and patient unavailability) may be allowed if agreed between the investigator and the sponsor.

If a patient misses a visit during which there is no treatment administration planned, the visit should be rescheduled as soon as possible, and the delayed visit documented with the actual date and the reason for the delay. The scheduling of subsequent visits must not be altered, so if it is not possible to reschedule prior to the next planned visit, the missed visit should be skipped.

If a patient is hospitalised for administrative reasons this will not be considered an SAE, unless any other criteria for an SAE are fulfilled.

In addition to the scheduled assessments, unscheduled visits and unscheduled assessments for safety reasons may be performed at any time according to clinical need.

In situations where a patient is unable or unwilling to attend a clinic visit, the investigator must assess the risk-benefit for the individual patient and may decide to perform a visit remotely if this is in the best interests of the patient and if agreed with the sponsor. Patient safety must be ensured when determining if a visit may be remote.

6.2 DETAILS OF TRIAL PROCEDURES AT SELECTED VISITS

The investigations as outlined in the [flowchart](#) will be performed at the respective visits. Specific details to conduct of physical examination, collection of vital signs, including blood pressure measurement, laboratory investigations, assessment of ECG, and other safety parameters can be found in the subsections of [section 5.2.2](#).

6.2.1 Screening and run-in period(s)

Screening Period

Patients may be consented to the clinical trial if they have imaging or other findings highly suggestive of a diagnosis of CRC. Such patients should subsequently undergo diagnostic and research biopsies in parallel, during screening, in order to avoid repeating procedures. Consented patients found to have a diagnosis other than CRC will be considered as screen-fail. Such patients will be replaced.

Following informed consent, the patient will undergo screening assessments as indicated in the [flowchart](#). The assessments must fall within the acceptable Screening visit window but do not need to be performed on the same day. Screening assessments may be repeated as long as they fall within the Screening visit window of 21 days. If more than one screening assessment is available, the latest assessment prior to the start of treatment must be used to assess eligibility.

Tumor assessments performed prior to informed consent as part of routine clinical practice will be accepted if they meet the requirements of the protocol and are performed within the Screening visit window of 21 days.

There is no mandatory order of assessments, but the biopsy must only be performed on patients who are expected to be eligible. Where applicable, the pre-treatment/baseline biopsy must be obtained prior to the dose.

If the patient meets the eligibility criteria during screening, the treatment visit should be scheduled. Any baseline conditions which are present at the Screening visit should be reported in the eCRF.

Re-screening of patients who have previously failed screening will be permitted. In this situation patients will be allocated a new patient number.

- During the screening visit, demographics information will be collected. This includes: age on the day of informed consent (in years)
- Sex (male, female in order to describe the subject's sex at birth)

Proprietary confidential information © 2022 Boehringer Ingelheim International GmbH or one or more of its affiliated companies

- Gender identity (male, female, other in order to describe how the subject self-identifies regardless of their genotypic or phenotypic sex)
- For women: of childbearing potential yes / no in order to characterize the patient population and as a basis for contraception requirements
- Pregnancy testing - serum
- Ethnicity and race in order to sufficiently characterize the patient population, to support possible subgroup analyses if needed unless not acceptable according to local regulations.
- Information on tobacco use

Baseline Conditions

Any baseline conditions which are present at the screening visit should be reported in the eCRF.

Demographics

Demographics (sex, birth year, race, and ethnicity [where allowed]), and baseline medical conditions will be collected during the screening visit.

Medical History of Cancer:

History of the patient's cancer will be obtained. The type of cancer, the date of the first histological diagnosis (month and year may be sufficient), and the primary tumor site will be reported on the eCRF. The differentiation grade, i.e. not specified, undifferentiated, poorly differentiated, moderately differentiated, well differentiated, obtained at screening, as well as the stage according to the tumor, lymph node, and metastasis (TNM) classification, will be provided as obtained at trial screening.

Other Medical History

Past diseases and/or concomitant diagnoses relevant to the patient's safety during the trial, assessment of biomarker such as PD-L1 expression, microsatellite instability (MSI), TMB information, and efficacy, as judged by the Investigator, will be recorded in eCRF.

Concomitant Medication

Past medications relevant to the patient's safety during the trial, as judged by the Investigator, will be recorded in the eCRF. From the date of signature of the main ICF, all concomitant medications will be recorded.

Please refer to the [Flowchart](#) for a detailed presentation of the Screening visit.

6.2.2 Treatment period(s)

In this trial the investigational combination treatment will be provided as single administration. Eligible patients will be administered study medication on Day 1.

Visit 1 (V01) – Day 1 (treatment day)

Patients in Cohort A will receive [REDACTED]

Patients in Cohort B will receive [REDACTED]

. Refer to

Table 3.1:1 for more details on treatments.

Patients will be allocated to Cohorts A and B alternatingly, with the first patient allocated to Cohort A and the second patient allocated to Cohort B. All eligible patients will be enrolled in the trial and genotyping will be performed retrospectively.

Patients must be observed for at least 4 hours post-infusion of study drugs, with immediate access to emergency resuscitation teams and equipment in addition to the ability to admit patients to an intensive care unit if necessary.

The following procedures are required at visit 1/Day 1

- Physical exam
- ECOG determination
- Adverse Events assessment
- Pregnancy testing (urine or serum)
- Standard labs (hematology/chemistry)
- Research blood samples

Visit 2 (V02) - [REDACTED]

The following procedures are required at visit 2/ [REDACTED]

- Physical exam
- ECOG determination
- Adverse Events assessments
- Research blood samples

Visit 3 (V03) - [REDACTED]

The patient will have a day of surgery scheduled per the patient's treatment. Within five (5) days and as close as possible prior to this surgery, the following procedures will be performed:

- Physical exam
- ECOG determination
- Adverse Events assessments
- Imaging
- Standard labs (hematology/chemistry)
- Research blood samples
- Stool sample (Note: on the day of before the surgery)

Proprietary confidential information © 2022 Boehringer Ingelheim International GmbH or one or more of its affiliated companies

- ***Resected tumor collection:** Tumor tissue will be a sample from the tumor removed during the surgery. (*Note: “Resected tumor collection” is listed under visit 3 in the flow chart for practical reasons and should occur at the **day of the surgery**. All other activities will be performed prior to the surgery.)

Please refer to the [Flow Chart](#) for a detailed presentation of each visit during Visits 1 through Visit 3.

6.2.3 Follow-up period and trial completion, End of Study (EOS) Visit

After the patient completes visit 1 through visit 3, there is a single visit to be conducted at \geq 91 days and no later than 120 days from Day 1. The following procedures need to be performed at the End of Study (EOS) Visit:

- Physical exam
- ECG
- ECOG determination
- Adverse Events assessments
- Research blood samples

After EOS visit, the patient has completed the trial and no further data collection is required.

If needed in the opinion of the investigator, after EOS visit, additional visits may be scheduled for continued safety monitoring. For information on follow-up period, see [section 7.2.6](#).

Abnormal assessments or lab values judged clinically relevant by the investigator will be monitored until they returned to a medically acceptable level.

7. STATISTICAL METHODS AND DETERMINATION OF SAMPLE SIZE

This is an open-label, two-arm, parallel group, single-center Phase 1 trial of ezabenlimab in combination with BI 765063 and Pembrolizumab in combination with BI 765063 in patients with early stage resectable colorectal cancer in neoadjuvant setting. Patients will be assigned alternately (sequentially one by one) to either of the cohorts and will receive one-time either of the combination treatments.

This is an exploratory study where the primary objective is to assess safety of patients treated with both the treatments in the neoadjuvant setting and also to ensure that the neoadjuvant treatment does not delay the recommended surgery. In addition, this trial will investigate efficacy as secondary objective and biological activity (including immunodynamic effect of the combined immunotherapy regimens systemically and on the tumor immune microenvironment) as further objectives.

7.1 NULL AND ALTERNATIVE HYPOTHESES

No formal hypothesis testing is planned in this trial. All the analyses in this trial are descriptive and exploratory. Results collected will be used for potential hypothesis generation. A Bayesian framework will be used to assess safety and feasibility. Any other analyses will be described in the Trial Statistical Analysis Plan (TSAP).

7.2 PLANNED ANALYSES

7.2.1 General considerations

For analyses of primary and secondary endpoints, all patients in the treated set (i.e., patients treated with one dose of trial medication) will be used if not specified differently. No per protocol set will be used in the analysis. However, important protocol violations will be identified and listed. Any other analysis set will be defined in the TSAP.

7.2.2 Handling of Intercurrent Events

Considering that patients will be treated with one-time treatment in both cohorts, no major intercurrent event is anticipated in this trial.

7.2.3 Primary objective analyses

The primary endpoint of the trial is a composite endpoint, safety and feasibility. Primary evaluation of safety and feasibility will be reported for all treated patients and will be measured as proportion of patients (along with 95% CI) who will meet the criterion of safety or feasibility (or both) defined in section 2.1.2. Safety and feasibility will be summarized separately for each arm.

In addition, safety and feasibility will be monitored, at interim and at final, using a Bayesian method. The incidence of complications after surgery for colorectal cancer is assumed approximately 20%. We consider that a neoadjuvant therapy with one of the regimens is not feasible if at least 20% of the patients with 85% or higher probability experience treatment related grade 3 or higher adverse events or have delay in surgery due to treatment related adverse events. Interim and final assessments for safety and feasibility will be conducted, separately, approximately after 5, 15 and 25 (final) patients being treated in each arm.

With a conservative prior probability of unfavorable “safety/feasibility” as Beta (0.1,0.4), the stopping boundaries are defined as seeing unfavorable “safety/feasibility” in ≥ 3 of first 5 patients, ≥ 5 of first 15, 8 or more out of 25 patients ([Table 7.2.3:1](#)). In case one arm needs to be closed due to unfavorable “safety/feasibility”, accrual to the remaining arm will continue. The calculation was performed using the Shiny Application: Bayesian Toxicity Monitoring version 2.2.1.0.

Table 7.2.3: 1 Early stopping boundary for unfavorable “safety/feasibility

# of patients (inclusive) per cohort	# of patients with related grade ≥ 3 AE or surgery delay	Decisions
5	3-5	Stopping
15	5-15	Stopping
25	8-25	Reached to final sample size

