1.4.2 Risks

Table 1.4.2: 1 displays the anticipated side effects of the study drugs, based on the mechanism of action, observed clinical data from ongoing studies, and published clinical data for drugs targeting SIRP α and PD-1 as well as the risk of trial procedures.

Table 1.4.2:1 Overview of trial related risks

Possible or known risks of clinical relevance for this trial	Summary of data, rationale for the risk	Mitigation strategy
Investigational Medicinal Products BI 765063 and ezabenlimab		
Unexpected adverse events and laboratory abnormalities	Due to limited clinical experience of the drugs.	Close monitoring of the data to ensure timely detection and reporting of any unexpected event. A Data Review Committee (DRC) will evaluate safety, feasibility, efficacy and biomarker results as available.
Immune-related adverse events (irAEs)	irAEs are associated with immune mediated mode of action and can be potentially severe.	Recommendations for the management of irAEs are provided according to international guidelines and product labels of approved PD-1 inhibitors [P19-00269]
Infusion related reactions (IRR)	As with any mAb, hypersensitivity reactions to study medication administration are possible and they are potentially severe.	Patients with history of severe hypersensitivity reactions to other mAbs are excluded. Recommendations for the management of infusion related reactions are given in Section 5.2.6.1.4
Drug Induced Liver Injury (DILI)	Rare but can be a potentially severe event, thus, under constant surveillance by sponsors for all drugs in development.	Timely detection, evaluation, and follow-up of laboratory alterations in selected liver laboratory parameters to ensure patients' safety.
Trial procedures		
Biopsies	Patients may experience biopsy related AEs such as pain or bleeding.	Site has to be selected based on ability and experience in performing all required trial procedures.

Possible or known risks of clinical relevance for this trial	Summary of data, rationale for the risk	Mitigation strategy
		The risks are clearly explained in the informed consent document.
Delay in surgery	Treatment related adverse events leading to delays in surgery	Patient will be monitored on an ongoing basis by the DRC for safety including treatment related events that may lead to a delay in surgery. The frequency of these events will be monitored, and enrolment will be adapted accordingly.

Potential risks related to BI 765063:

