3.1.1 Data review committee (DRC)

A total of approximately 50 patients will be treated in this trial, i.e. approximately 25 patients in each arm. A Data Review Committee (DRC) will be established to oversee and assess the progress of the clinical trial, specifically for safety, feasibility, efficacy and biomarker results as available. The DRC will operate according to specifications defined in a separate DRC charter.

The DRC will consist of the following members:

- Principal Investigator (PI), decision maker
- BI Safety physician (pharmacovigilance officer), decision maker
- BI Clinical Program Leader (CPL), decision maker,
- BI Statistician (Stat), participates if needed
- BI Clinical Trial Leader (CTL), participates if needed

All members can be represented by a deputy.

The first scheduled DRC meeting to review data will take place after approximately 5 patients in each arm have been treated, and while recruitment continues. A second meeting of the DRC will be scheduled to review the data after approximately 15 patients have been treated in each arm. After each of these meetings the DRC will recommend to continue, to modify, or to stop the trial due to any safety concern. The DRC may meet to review data any other time if deemed necessary.

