7.2.8 Interim Analyses

Two interim analyses are planned to assess safety and feasibility of the treatments. A Bayesian framework will be used to assess safety and feasibility after, approximately, 5 and 15 patients are treated in each arm. A Data Review Committee (DRC) will review the overall data along with the results from Bayesian calculation at interim.

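### The safety/feasibility boundary is tied to three fixed looks, and no count triggers a hold once crossing at the next look is already certain

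*Protocol*

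**What the plan says.** Protocol section 7.2.3 defines the boundary for each arm as unfavourable events in "≥ 3 of first 5 patients, ≥ 5 of first 15, 8 or more out of 25 patients". The assessments take place "approximately after 5, 15 and 25 (final) patients being treated in each arm". The counts come from a posterior rule under a Beta(0.1, 0.4) prior: a regimen is judged "not feasible if at least 20% of the patients with 85% or higher probability experience" a related grade 3 or higher event or a treatment-related delay in surgery. In Table 7.2.3:1 the rows for 5 and 15 patients carry a stopping decision, while the row for 25 reads "Reached to final sample size". Section 7.2.8 confirms the number of formal interims: "Two interim analyses are planned to assess safety and feasibility of the treatments".

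Other parts of the protocol allow earlier action:

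- Section 3.1.1: "The DRC may meet to review data any other time if deemed necessary". The same section has recruitment continuing through the first scheduled review and refers operating details to a separate charter.
- Section 1.4.2, delay-in-surgery row of Table 1.4.2:1: ongoing monitoring by the DRC, and "The frequency of these events will be monitored, and enrolment will be adapted accordingly".
- Section 1.4.3: continuous safety monitoring, with serious, immune-related and special-interest events taken to the DRC as needed.

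None of these gives a number of events that holds accrual.

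**The concern.** A cumulative event count can only rise. Suppose an arm has 2 events in its first 5 patients and then events in patients 6, 7 and 8. It now has 5 events, so the 15-patient boundary will be met whatever happens to the next 7 patients. The written rule nevertheless looks next at patient 15. The same can happen before the 5-patient look and between patients 15 and 25.

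These patients have resectable disease, and section 7 gives not delaying their surgery as part of the primary aim. Treating more of them in an arm that is already certain to meet the sponsor's own unfavourable criterion adds exposure without changing the boundary decision. The gap does not depend on pending outcomes: it exists even when every outcome is known.

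**Working it through.** **Inputs.** Looks at 5, 15 and 25 treated patients per arm; boundary counts 3, 5 and 8; prior Beta(0.1, 0.4); threshold rate 0.20; posterior cut-off 0.85 (all section 7.2.3); operating characteristics from Table 7.5:1 (section 7.5).

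**Step 1: reproduce the boundary.** With r events in n patients, find the smallest r for which P(rate > 0.20 | Beta(0.1 + r, 0.4 + n − r)) is at least 0.85.

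- n = 5: 0.807 at r = 2, 0.967 at r = 3. Boundary 3.
- n = 15: 0.695 at r = 4, 0.866 at r = 5. Boundary 5.
- n = 25: 0.809 at r = 7, 0.909 at r = 8. Boundary 8.

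The stated counts are right.

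**Step 2: reproduce Table 7.5:1 with fixed looks.** An exact binomial recursion over the three looks gives the stopping probabilities. Average N = 5 × P(stop at 5) + 15 × P(stop at 15) + 25 × (1 − both). At a true rate of 40%: 5 × 0.3174 + 15 × 0.4764 + 25 × 0.2061 = 1.59 + 7.15 + 5.15 = 13.89, against 13.88 in the table.

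**Step 3: act at the same counts when they are reached.** A patient-by-patient recursion holds the arm at the 3rd event within the first 5 patients, the 5th within the first 15, or the 8th within 25. Every arm that meets a boundary under one rule meets it under the other, so the declare probability is identical.

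| True rate | Table 7.5:1: early stop / declare / average N | Exact, fixed looks | Average N, acting at the count | Saving per arm |
|---|---|---|---|---|
| 10% | 0.01 / 0.02 / 24.72 | 0.019 / 0.020 / 24.73 | 24.70 | 0.02 |
| 20% | 0.18 / 0.21 / 22.57 | 0.184 / 0.215 / 22.58 | 22.24 | 0.34 |
| 30% | 0.50 / 0.60 / 18.31 | 0.505 / 0.605 / 18.32 | 17.17 | 1.15 |
| 40% | 0.79 / 0.89 / 13.88 | 0.794 / 0.893 / 13.89 | 11.94 | 1.95 |
| 50% | 0.94 / 0.98 / 10.55 | 0.944 / 0.986 / 10.56 | 8.29 | 2.27 |

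At 40% the saving splits into 0.24 before the 5-patient look, 1.49 before the 15-patient look and 0.22 before the end: 0.24 + 1.49 + 0.22 = 1.95.

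**Step 4: how often, and how far.** The probability that at least one patient is treated after crossing is certain is 0.01, 0.14, 0.44, 0.68 and 0.77 at true rates of 10% to 50%. Among arms that stop at 15, the mean overrun is 2.0, 2.5, 3.1 and 3.9 patients at 20% to 50%. The largest possible overrun in each stretch is:

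- 5 − 3 = 2 before the first look (events in patients 1 to 3);
- 15 − 8 = 7 before the second (2 events by patient 5, then events in patients 6 to 8);
- 25 − 19 = 6 before the last (4 events by patient 15, then events in patients 16 to 19).

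**Step 5: allow for delayed recognition.** Step 3 assumes each outcome is known before the next patient is treated. The protocol gives no accrual rate, so a lag has to be assumed. Suppose the hold takes effect some patients after the count is reached, and no later than the next look, while the fixed looks have no lag. The saving per arm at 40% and 50% is then about 0.8 and 1.0 for a lag of two patients, 0.2 and 0.3 for four, and 0.02 and 0.04 for six. At 20% it is 0.11 for a lag of two.

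**Step 6: effect on the rate estimate.** With no lag, the mean observed event rate rises from 0.47 to 0.50 at a true 40%, and from 0.57 to 0.60 at a true 50%.

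**The case against.** The strongest reply is that the protocol is not blind between looks. The DRC monitors continuously, may meet at any time, and is told to adapt enrolment to surgery-delay events. Serious and special-interest events are reported within 24 hours (section 5.2.6.2.1). The trial is open-label at one planned centre, and the principal investigator is a DRC decision maker. An arm running from patient 8 to patient 15 with 5 events on record would need all of this to fail, and the charter may contain a trigger. This stands as a limit on the point. A reader might infer that an arm *will* go on treating after its count is reached; the documents support only that it *can*. The safeguards permit a hold but attach no number to it, and the enrolment sentence sits in the surgery-delay row alone.

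A second reply is that a condition on the first 15 patients is literally met at the 5th event, whenever it occurs. However, section 7.2.3 places the assessments at the looks, and Table 7.5:1 matches only that reading: at 40% its average of 13.88 agrees with 13.89 for fixed looks, not with 11.94.

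A third is that fixed looks are conventional and their cost is disclosed. That is correct. A reader might infer that Table 7.5:1 is wrong or hides the overrun. It does neither, since the extra patients are already in its average.

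A fourth is that waiting has some statistical value. That also stands. The primary analysis is a proportion with a 95% confidence interval, and holding at an event makes it less precise and pushes it slightly upward (Step 6). Waiting has no value for the boundary decision, but it does have some for estimation.

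**Conclusion.** The point holds as a design weakness of modest size that is cheap to repair. Nothing readable in the protocol ties a hold on accrual to an event count between looks, so an arm can treat up to 7 further patients after crossing at the 15-patient look is certain.

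The savings in Step 3 are upper limits that rest on immediate outcomes. It would be tempting to double them and promise about 4 to 4.5 fewer patients over two arms at true rates of 40–50%. The documents do not support that as an expectation: the safety window is 90 days, surgery falls 2 to 6 weeks after dosing, and recruitment continues through the first review. About 0.8 to 1.0 per arm is the figure at those rates under an assumed two-patient lag with no lag at the fixed looks, and longer lags shrink it further. If the fixed looks also wait for outcomes while accrual goes on, they overrun too and more of the saving is kept. At the protocol's own 20% threshold the saving is at most 0.34 per arm.

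The SAP (sections 3 and 6.4) records that the trial ended early with two treated patients, so no look was reached and no result is affected. The point matters if the design is used again.

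**What to change.** Add to sections 7.2.3 and 3.1.1 and to the DRC charter, unless the charter already says so: *Accrual to an arm is held and the DRC is convened as soon as the 3rd event among its first 5 treated patients, the 5th among its first 15, or the 8th among its 25 is reported.* Keep the boundary counts, the looks and the prior.

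This is not the same as applying the 85% posterior rule after every patient. Doing that from patient 5 onward would raise the declare probability to 0.04 at a true 10% and to 0.30 at a true 20%. The proposed wording leaves it where it is.

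In Table 7.5:1, recompute four columns; the declare column does not change. With no lag, at a true 40%:

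- early stop: 0.79 becomes 0.87, counting holds between patients 16 and 24 as early;
- average patients: 13.88 becomes 11.94;
- average events: 5.55 becomes 0.4 × 11.94 = 4.78;
- observed rate: 0.47 becomes 0.50.

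The cost is one sentence, a running event count at a single site and an occasional unscheduled DRC meeting. The event rate in an arm that has already met its boundary would be less precise and slightly more biased upward.
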